2.1 Risk/Benefit Assessment

2.1.1 Known Potential Risks

The most common adverse reactions with BIC/F/TAF (incidence greater than or equal to 5%, all grades) are diarrhea, nausea, and headache. Other potential warnings and precautions include the immune reconstitution syndrome, new onset or worsening renal impairment, and lactic acidosis/severe hepatomegaly with steatosis.

2.1.2 Known Potential Benefits

BIC/F/TAF has demonstrated high rates of virologic suppression and no treatment-emergent resistance through 48 weeks in phase 3 clinical trials among treatment naïve adults and among virologically suppressed adult patients who switched ARV regimens. BIC/F/TAF also has lower pill burden than other anti-retroviral regimens, due to a one-pill composition.

3. Study Design

3.1 Overall Design

We hypothesize that BIC/F/TAF will be efficacious and safe in the management of HIV+ post renal transplant patients, and will have few adverse reactions and drug-drug interactions with tacrolimus in this population.

Eighteen subjects will be enrolled in this Phase IV, single arm, open-label, single-site, switch study. In this study, virally suppressed HIV+ adults will be switched post-renal transplant from their current anti-retroviral regimen to BIC/F/TAF and will be followed for 48 weeks with a 6 month follow-up (Section 6.1). Informed consent will be obtained before starting the study (Section 6.1).

Patients will have bloodwork completed throughout the study, as shown in the Schedule of Assessments (Section 6.1).

A health-related quality of life questionnaire (Appendix) will be administered to each patient to assess satisfaction with a one pill regimen as well as adverse events (Section 6.1).

Pharmacokinetic (PK) studies will be assessed at Week 12 when the renal function is stable (decided by PI). Intracellular TAF levels by dried blood spot will be collected during the Week 12 visit as well as Week 24, Week 36, Week 48, Month 6 Follow-up. Intracellular TAF levels by PBMC will be collected once during the Week 12 visit. An intensive pharmacokinetic day will take place at the Week 12 visit. This bloodwork is outlined in Section 6.1. Bloodwork for the intracellular TAF level testing and pharmacokinetic testing will be stored and sent to [name] at the University of Colorado's Antiviral Laboratory. (14-16)

Note: Patients switched post-renal transplant from their current anti-retroviral regimen to BIC/F/TAF prior to identification for this study may also be enrolled. This group will be referred to as "Group 2". Pharmacokinetic testing for Group 2 subjects will be completed once each Group 2 subject's tacrolimus levels are stable as per the Principal Investigator for 2-4 weeks. All standard of care lab values and concomitant medications will be collected from Group 2 subjects for 60 days prior to and after the Biktarvy switch date and for the duration of Biktarvy therapy. Any adverse events related to Biktarvy prior to enrollment will be recorded.

Sample Collection

Samples include plasma and peripheral blood mononuclear cells (PBMC). Blood is collected in EDTA tubes for plasma separation. CPT vacutainers are used to isolate PBMC, which are counted with an

automated countess cytometer (Invitrogen™, Thermo Fisher Scientific Corporation, Carlsbad, CA) and lysed. BIC, F, and TAF in plasma are assayed using a validated LC/MS/MS methodology with a lower limit of quantification (LLOQ) of 10 ng/mL (16).

Determination of Pharmacokinetic Variables

The pharmacokinetic variables for BIC/F/TAF are calculated from the concentration-time data using noncompartmental methods. The peak drug concentration (C_{max}) and time of peak drug concentration are obtained directly from the observed data. The terminal elimination rate constant (k_{el}) is obtained from a log-linear regression of the plasma concentration compared to time data in the terminal post distribution phase. The elimination half-life ($t_{1/2}$) is calculated from $0.693/k_{el}$. The area under the plasma drug concentration-versus-time curve (AUC_{0-24}) and the area under the moment curve from 0 to 24 h ($AUMC_{0-24}$) are calculated by the log-linear trapezoidal rule. The area under the plasma drug concentration-versus-time curve from time zero to time infinity ($AUC_{0-\infty}$) is obtained from the following equation: $AUC_{0-24} \cdot C_t/k_{el}$, where C_t is the last measurable concentration and k_{el} is the terminal elimination rate constant. The total body clearance (CL) is obtained from the equations $dose/AUC_{0-\infty}$ and $dose/AUC_{0-24}$ (presumed steady state, where 24 h is the dosing interval), respectively. The volume of distribution (V_d) is calculated as follows: $V_d = CL/k_{el}$. The steady-state volume of distribution (V_{ss}) is calculated from the product of CL and the mean residence time. The mean residence time is obtained from the following equation: $(AUMC_{0-\infty}/AUC_{0-\infty}) T/2$, where $AUMC_{0-\infty}$ is extrapolated from $[(C_t \times t)/k_{el} \times C_t/k_{el}]$ and where T is the infusion time, all other terms having been previously defined.

Statistical Analyses and Sample Size

This is a pilot study of the efficacy, safety, and pharmacokinetics of BIC/F/TAF in HIV+ renal transplant recipients. Sample size is based upon feasibility of enrolling the current cohort of patients on the WCM/NYPH renal transplant service who are currently receiving antiretroviral therapy. Among the 37 HIV+ renal transplant recipients who are followed at NYPH and who are currently eligible for the study, we project that 20 patients will enroll into this study and complete treatment.

We hypothesize that in the transition from a standard antiretroviral regimen to a BIC/F/TAF regimen, there would be high probability of a sustained suppression of HIV- RNA (1). In the randomized, double-blind, multicenter, active-controlled, phase 3, non-inferiority clinical trial of switching to fixed-dose bictegravir, emtricitabine, and tenofovir alafenamide from dolutegravir plus abacavir and lamivudine in virologically suppressed adults with HIV-1 by Molina et al, the primary endpoint was the proportion of participants with plasma HIV-1 RNA of 50 copies per mL or higher at week 48 that fulfilled the prespecified non-inferiority margin of 4%, where three (1%) of 282 in the bictegravir group had HIV-1 RNA of 50 copies per mL or higher at week 48 versus one (<1%) of 281 participants in the dolutegravir group (difference 0.7%, 95.002% CI -1.0 to 2.8; $p=0.62$).

The number of 20 subjects who are projected for enrollment and study completion will provide sufficiently robust data for pharmacokinetic studies to yield a coefficient of variation of <15%, which will permit a robust analysis and model development.

Outcome variables and adverse events will be reported using descriptive statistics, including means, medians, ranges, and standard errors.

The relationship between renal function, tacrolimus levels, BIC/F/TAF plasma concentrations, and intracellular concentrations of TAF will be determined by linear regression analysis.

4. Subject Selection

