Pharmacokinetic (PK) studies will be assessed at Week 12 when the renal function is stable (decided by PI). Intracellular TAF levels by dried blood spot will be collected during the Week 12 visit at 0, 4, and 24 hours post-dose (the 24 hour time point is optional, if feasible). Additionally, 1 sample will be collected at Week 24, Week 36, Week 48, Month 6 Follow-up. Over the course of the study, 7 dried blood spot collections will be completed per patient. Intracellular TAF levels by PBMC will be collected once during the Week 12 visit at 0, 4, and 24 hours post-dose (the 24 hour time point is optional, if feasible). An intensive pharmacokinetic day will take place at the Week 12 visit, during which up to 7 samples will be collected at 0, 0.5, 1, 2, 4 and 24 hours post-dose (the 24 hour time point is optional, if feasible). This bloodwork is outlined in Section 6.1. Bloodwork for the intracellular TAF level testing and pharmacokinetic testing will be stored and sent to [name] at the University of Colorado's Antiviral Laboratory. (14-16)

A health-related quality of life questionnaire (Appendix) will be administered to each patient to assess satisfaction with a one pill regimen as well as adverse events (Section 6.1).

If a subject needs to stop treatment as per the Data and Safety Monitoring Plan (Section 12), the subject will be seen as soon as possible for an Unscheduled Visit and will continue to be followed for the duration of the study as per the Schedule of Assessments for non-terminated patients.

If services outside of the study (standard of care, or "SOC") are completed for a patient during the study period, only the research-related tests and procedures will be billed to the study, regardless of study visit date overlap. SOC tests and procedures are expected throughout the study period for this population.

Sample Collection

Samples include plasma and peripheral blood mononuclear cells (PBMC). Blood is collected in EDTA tubes for plasma separation. CPT vacutainers are used to isolate PBMC, which are counted with an automated countess cytometer (Invitrogen™, Thermo Fisher Scientific Corporation, Carlsbad, CA) and lysed. BIC, F, and TAF in plasma are assayed using a validated LC/MS/MS methodology with a lower limit of quantification (LLOQ) of 10 ng/mL (16).

7. Study Intervention

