10.1 Study Design/Endpoints

We hypothesize that in the transition from a standard antiretroviral regimen to a BIC/F/TAF regimen, there would be high probability of a sustained suppression of HIV- RNA (1). In the randomized, double-blind, multicenter, active-controlled, phase 3, non-inferiority clinical trial of switching to fixed-dose bicitegravir, emtricitabine, and tenofovir alafenamide from dolutegravir plus abacavir and lamivudine in virologically suppressed adults with HIV-1 by Molina et al, the primary endpoint was the proportion of participants with plasma HIV-1 RNA of 50 copies per mL or higher at week 48 fulfilled the prespecified non-inferiority margin of 4%, where three (1%) of 282 in the bicitegravir group had HIV-1 RNA of 50 copies per mL or higher at week 48 versus one (<1%) of 281 participants in the dolutegravir group (difference 0.7%, 95.002% CI-1.0 to 2.8; p=0.62).

The number of 20 subjects who are projected for enrollment will provide sufficiently robust data for pharmacokinetic studies to yield a coefficient of variation of <15%, which will permit a robust analysis and model development. Outcome variables and adverse events will be reported using descriptive statistics, including means, medians, ranges, and standard errors. The relationship between renal function, tacrolimus levels, BIC/F/TAF plasma concentrations, and intracellular concentrations of TAF will be determined by linear regression analysis.

Expected Outcomes:

1. We expect sustained suppression of the HIV viral load throughout the study.
2. We expect that BIC/F/TAF will be well tolerated in the HIV+ renal transplant population with minimal adverse events and preservation of renal function with stable tacrolimus levels.
3. Plasma concentrations of BIC/F/TAF will follow those reported in HIV+ non-renal transplant recipients and drug/drug interactions with tacrolimus will be minimal, allowing easy adjustment with minimal detrimental effects on renal function.

11. Adverse Events

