11.6 AE/SAE Follow Up

All SAEs and AEs reported during this study will be followed until resolution or until the investigator confirms that the AE/SAE has stabilized and no more follow-up is required. This requirement indicates that follow-up may be required for some events after the subject discontinues participation from the study.

12. Data and Safety Monitoring Plan (DSMP)

The WCM DSMB will be used for this investigator-initiated study. The following information will be submitted to the WCM DSMB every 6 months from the time of the first enrollment:

Laboratory results

- T-lymphocytes, HIV viral load: From Day 1, Week 4, Week 12, Week 24, Week 36, Week 48, 3-month Follow-up, and 6-month Follow-up
- Select clinical safety labs¹: From Day 1 and all visits from Week 4 through 6-month Follow-up

- BUN, creatinine: From Days 3 through Day 22, and if needed at additional time points, as per investigator
- Tacrolimus levels: All time points
- Any HIV-resistance testing needed, as per investigator

¹Clinical Safety Labs include: CBC, complete metabolic panel, urinalysis, eGFR

Adverse Events and Stopping Rules

The following adverse events will be submitted to the WCM DSMB and may cause the subject to terminate protocol treatment:

1. Severe drug reaction, including rash or fever (as determined by the PI)
2. Inability to control tacrolimus levels, as defined by the primary renal transplant provider, which may lead to renal graft failure
3. ALT or AST > 5 x ULN
4. Virologic failure, as determined by the Principal Investigator, which would be defined as: On-treatment HIV-1 RNA ≥ 50 copies/mL twice sequentially, separated by 4-6 weeks
5. Development of documented resistance to BIC/FTC/TAF

Renal dysfunction requiring evaluation is defined as a decrease in creatinine clearance to CrCl < 30 mL/min. The evaluation of renal dysfunction will be completed by the primary renal transplant team, in conjunction with the PI.

If the CrCl is below 30 mL/min, the BIC/F/TAF will be held and an evaluation will be performed by the primary renal transplant physician in conjunction with the PI. The evaluation of the cause will be explored by the primary renal transplant physician in conjunction with the PI. The patient will be discontinued from the study at the discretion of the PI, after discussion with the primary renal transplant physician, if deemed necessary.

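### The regression linking drug levels, tacrolimus and renal function has no stated unit of analysis; if repeated visits were pooled, standard errors would be about 1.2 to 2.7 times too small under assumed correlations

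*Combined protocol and SAP*

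**What the plan says.** Section 3.1 (Statistical Analyses and Sample Size) states: "The relationship between renal function, tacrolimus levels, BIC/F/TAF plasma concentrations, and intracellular concentrations of TAF will be determined by linear regression analysis." Section 10.1 repeats the sentence, ending "intracellular concentrations of TAF will be determined by linear regression analysis," and adds no detail. Neither place says which variable is the outcome, which visits enter, or what one row of the dataset is. No mixed model, GEE, cluster-robust standard error or per-subject summary is named for this analysis.

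The variables are collected on different schedules (Section 6.1):

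- **Tacrolimus:** 11 non-optional visits (Day 1; Weeks 4, 8, 12, 16, 24, 32, 36, 48; follow-up Months 3 and 6), plus up to four optional visits from Day 3 to Day 22. Section 12 lists "Tacrolimus levels: All time points" among the data for the monitoring board.
- **Renal function:** eGFR is one of the clinical safety labs, which Section 12 describes as "From Day 1 and all visits from Week 4 through 6-month Follow-up". That is the same 11 visits.
- **Dried blood spot TAF:** "Over the course of the study, 7 dried blood spot collections will be completed per patient", at 5 visits.
- **PBMC TAF and plasma BIC/F/TAF:** the PK day only. Section 3.1 says "Intracellular TAF levels by PBMC will be collected once during the Week 12 visit", and the six plasma time points are also at Week 12. For Group 2 the PK day depends on stable tacrolimus levels.

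On numbers of subjects, Section 3.1 says "we project that 20 patients will enroll into this study and complete treatment" but also "Eighteen subjects will be enrolled in this Phase IV, single arm, open-label, single-site, switch study".

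**The concern.** Standard linear regression treats each row as independent. Repeated tacrolimus, eGFR or dried blood spot values from one person are likely to resemble one another more than values from different people. Twenty subjects at 5 visits give 100 rows, and at 11 visits 220 rows, but neither dataset carries that many independent pieces of information about how subjects differ. A model that ignores this reports intervals that are too narrow.

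Regression is the only method named for relating drug levels to tacrolimus and renal function. That relation bears on the third primary objective (interaction with tacrolimus) and on the second specific aim in Section 1.2. The Background says it is unknown whether tenofovir accumulates and harms the kidney alongside tacrolimus. A falsely precise slope could suggest an association that is not there, or make an imprecise null result look firm.

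**Working it through.** **1. The plan's own figures.** The sample size of 20 rests on feasibility; no alpha, power, SD or intraclass correlation (ICC) is given, so there is no calculation to reproduce. The dried blood spot count does reproduce: 3 samples at Week 12 (0, 4 and an optional 24 hours), plus one each at Weeks 24, 36 and 48 and Month 6, is 3 + 1 + 1 + 1 + 1 = 7 samples at 5 visits.

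**2. Records per subject, m.** A relation across visits that involves dried blood spot TAF has m = 5 visits. Tacrolimus against renal function has m = 11.

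**3. Formula.** For a pooled slope with exchangeable correlation within subjects, the true standard error divided by the reported one is about

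ratio = sqrt(1 + (m − 1) × ICC_x × ICC_y),

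where ICC_x and ICC_y are the intraclass correlations of predictor and outcome. Both appear because tacrolimus, eGFR and dried blood spot TAF all change from visit to visit.

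**4. Results.** The ICCs are assumptions, taken as equal for both variables.

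| ICC (both) | m = 5 | m = 11 |
|---|---|---|
| 0.3 | sqrt(1 + 4 × 0.09) = 1.17 | sqrt(1 + 10 × 0.09) = 1.38 |
| 0.5 | sqrt(1 + 4 × 0.25) = 1.41 | sqrt(1 + 10 × 0.25) = 1.87 |
| 0.8 | sqrt(1 + 4 × 0.64) = 1.89 | sqrt(1 + 10 × 0.64) = 2.72 |

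**5. Simulation check.** With 20 subjects, a true slope of zero and 4,000 runs per setting, the ratios for ICCs of 0.3, 0.5 and 0.8 were 1.15, 1.41 and 1.94 at m = 5, and 1.37, 1.89 and 2.78 at m = 11. A nominal 5% test rejected 9%, 16% and 30% of the time at m = 5, and 15%, 30% and 50% at m = 11. With 18 subjects the results were close (ratios 1.17, 1.43, 1.89 and 1.36, 1.87, 2.79), so the conflict between 18 and 20 barely matters here.

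**6. One record per subject.** With m = 1 the formula gives exactly 1. The simulation gave 1.01 to 1.04 and about 5% rejection at 20 subjects.

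**7. Sensitivity.** If the predictor were constant within subject (ICC_x = 1), ICC_y of 0.3 to 0.8 would give sqrt(1 + 4 × 0.3) = 1.48 to sqrt(1 + 4 × 0.8) = 2.05 at 5 visits, and sqrt(1 + 10 × 0.3) = 2.00 to sqrt(1 + 10 × 0.8) = 3.00 at 11. If the predictor had no stable between-subject component (ICC_x = 0), the ratio would be 1.

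**The case against.** A reader might infer that the plan commits to ordinary least squares on pooled visits, with standard errors 1.5 to 3 times too small. The documents do not support that. They say only linear regression, and pooling is an inference. A Week 12 reading fits the wording equally well: the synopsis sets the PK and tacrolimus objective at 12 weeks, plasma and PBMC samples are scheduled only on the PK day, and the plasma data are reduced to one set of noncompartmental parameters per subject. The 1.5 to 3 range also needs a predictor that is constant within subject. Its upper end needs 11 visits and very high correlation, and no relation involving intracellular TAF has more than 5 visits.

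Other points in the plan's favour stand as well. Subject means or separate regressions at each visit would also avoid the problem. Noncompartmental and descriptive methods are named for PK, so regression is the sole named method only for the associations. The dried blood spots have a second purpose, monitoring adherence. The Section 12 lists describe data sent to the monitoring board, so they confirm collection but do not define the regression dataset. This is a pilot with no stated alpha or regression hypothesis.

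The Week 12 reading still does not settle the matter. The plan never states it, and the Background speaks of serial plasma and PBMC sampling over 48 weeks. The fourth primary objective places tacrolimus and renal biomarkers at 24 and 48 weeks, which a Week 12 regression cannot relate to drug levels. Even on the PK day there are up to 6 plasma, 3 PBMC and 3 dried blood spot samples per subject, and the regression sentence names concentrations rather than AUC or Cmax.

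**Conclusion.** The concern holds in a limited form. The plan names linear regression for variables that are largely repeated within about 20 subjects, and it leaves both the unit of analysis and the within-subject correlation unaddressed. If visits were pooled, standard errors would be too small by about 1.2 to 1.9 times for dried blood spot TAF relations and 1.4 to 2.7 times for tacrolimus against renal function. This assumes exchangeable correlation and equal ICCs of 0.3 to 0.8. If the regression were confined to one Week 12 record per subject, clustering would cause no understatement, but the later spots would not inform the relation.

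The consequence is over-precise intervals or p-values for exploratory associations. It would be wrong to conclude that the main efficacy result is compromised: the week 48 HIV RNA proportion does not depend on this regression. The point merits a change to the plan because a suitable method is readily available and needs no new data.

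**What to change.** Replace the single sentence in Sections 3.1 and 10.1 with two specifications, and name the outcome and predictor for each relation.

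- **Relations involving plasma or PBMC measures:** linear regression with one record per subject from the PK day, for example AUC or trough, with the chosen summary stated in advance.
- **Relations across visits (dried blood spot TAF, tacrolimus, renal function):** a linear mixed model with a random intercept for subject, log-transformed concentrations, and a small-sample degrees-of-freedom correction such as Kenward-Roger. Enter time since switch rather than visit number, because Group 2 subjects join the schedule at the investigator's discretion and a given visit does not mark a common time on treatment.

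GEE with a small-sample correction would be an acceptable alternative for the second item. The cost is a few sentences in the plan, slightly more analysis work, and wider intervals than a pooled regression would show. No extra visits or samples are needed.

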4.1 Study Population

Virally suppressed HIV+ adults post-renal transplant who meet the inclusion and exclusion criteria will be eligible for participation in this study.

4.2 Inclusion Criteria

1. Be ≥ 18 years of age on day of signing informed consent.
2. Have documented positive results for human immunodeficiency virus (HIV) antibody (HIV-Ab) test at time of enrollment.
3. Received a previous renal transplant.
4. Must have controlled HIV infection, defined as HIV-1 RNA < 50 copies/ml for ≥ 3 months prior to enrollment.

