4.3 Exclusion Criteria

1. Has renal function of CrCl < 30 mL/min at time of enrollment. CrCl will be calculated using the Cockcroft-Gault equation using the most recently obtained and available serum creatinine value collected.
2. BIC/F/TAF is the only antiretroviral therapy ever used for treatment of HIV infection.
3. Is allergic to any of the HIV meds in BIC/F/TAF (bictegravir, emtricitabine, or tenofovir alafenamide).
4. Pregnant or breastfeeding.
5. Is currently taking dofetilide or rifampin.
6. Has severe hepatic impairment (Child-Pugh Class C).
7. ALT or AST $> 5 \times$ ULN.

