4.5 Screen Failures

Screen failures are defined as participants who consent to participate in the clinical trial but are not subsequently entered in the study. A minimal set of screen failure information is required to ensure transparent reporting of screen failure participants, to meet the Consolidated Standards of Reporting Trials (CONSORT) publishing requirements and to respond to queries from regulatory authorities. Minimal information includes demography, screen failure details, eligibility criteria, and any serious adverse event (SAE).

Individuals who do not meet the criteria for participation in this trial (screen failure) because of a renal function value exclusion may be rescreened. Rescreened participants should be assigned the same participant number as for the initial screening.

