6.1 Schedule of Assessments*

Activity	D 1	D 3	D 8	D 15	D 22	W 4	W 8	W 12	W 16	W 24	W 32	W 36	W 48	FU – M3	FU – M6	UV ^k	
Visit Window (Days)	±1	±3				±7											
Informed consent	X ^a																
Inclusion/Exclusion Criteria	X																
Research study visit, including weight	X	X ⁱ	X ^j	X ^j	X ^j	X	X	X	X	X	X	X	X	X	X	X	
Physical exam	X					X ^b		X ^b		X		X ^b	X	X ^b	X ^b	X ^b	
Questionnaire booklet administration	X																
Questionnaire completion ^c						X		X		X		X	X	X	X	X	
Dispense study medication	X										X						
T-lymphocytes, HIV viral load	X					X		X		X		X	X	X	X	X	
HIV-resistance testing		As needed, as per investigator ^d															
Tacrolimus level	X	X ⁱ	X ^j	X ^j	X ^j	X	X	X	X	X	X	X	X	X	X	X	
BUN, creatinine		X ⁱ	X ^j	X ^j	X ^j	As needed, as per investigator ^e											
Clinical Safety Labs ^f	X					X	X	X	X	X	X	X	X	X	X	X	
TAF levels, intracellular (dried blood spot) ^g								X		X		X	X		X	X	
TAF levels, intracellular (PBMC) ^h								X									
Pharmacokinetics ⁱ								X									

Abbreviations: D = Day; W = Week; M = Month; FU = Follow-up; UV = Unscheduled Visit

*If services outside of the study (standard of care, or "SOC") are completed for a patient during the study period, only the research-related tests and procedures will be billed to the study. SOC tests and procedures are expected throughout the study period for this population.

^a Informed consent may be obtained up to 2 months before D1. Subjects enrolled into Group 2 will begin the study schedule at the Day 1 visit and will then be inserted into the Schedule of Assessments at the discretion of the Principal Investigator based on stability of the subject's HIV viral load and tacrolimus levels.

^b If there are complications, as deemed by the investigator, a physical exam will be conducted at this time point. If institutional restrictions limit outpatient visits, the most recent physical exam completed by the primary care physician will be used to avoid direct contact or exposure of patients.

^c Questionnaires may be completed by phone or returned by mail, if institutional restrictions limit outpatient visits.

^d HIV resistance testing will be performed if there are two consecutive breakthrough HIV viral loads >50 copies/mL, spaced 4-6 weeks apart.

^e Additional BUN and/or creatinine labwork may be drawn at these timepoints, if deemed necessary for safety purposes by the investigator.

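### Group 2 is screened for eligibility after its switch to BIC/F/TAF, so pooling it with prospectively switched subjects tilts the results in favour of BIC/F/TAF

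*Combined protocol and SAP*

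**What the plan says.** The note in Section 3.1 opens the study to a second group: "Patients switched post-renal transplant from their current anti-retroviral regimen to BIC/F/TAF prior to identification for this study may also be enrolled". One set of criteria covers everyone. Section 4.1 states "Virally suppressed HIV+ adults post-renal transplant who meet the inclusion and exclusion criteria will be eligible for participation in this study", and Sections 4.2 and 4.3 have no version for Group 2.

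The time anchors are these:

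- **Viral load (inclusion 4):** "Must have controlled HIV infection, defined as HIV-1 RNA < 50 copies/ml for ≥ 3 months prior to enrollment".
- **Renal function (exclusion 1):** "Has renal function of CrCl < 30 mL/min at time of enrollment", using the latest available creatinine.
- **Transaminases (exclusion 7):** ALT or AST above 5 × ULN, with no date given. I read it as applying at enrolment too.

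None of the three refers to the switch date. Section 12 uses the same thresholds during treatment. Two sequential values of 50 copies/mL or more, 4–6 weeks apart, are virologic failure, and ALT or AST above 5 × ULN is an event that may end treatment. For renal function, "If the CrCl is below 30 mL/min, the BIC/F/TAF will be held" pending evaluation.

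The primary efficacy endpoint is a single proportion of subjects suppressed at week 48. Section 10.1 plans descriptive reporting and does not separate the two groups.

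**The concern.** The trial asks whether switching is efficacious, safe and tolerated. That calls for following people from the switch onward. A subject switched at Day 1 who rebounds, falls below the CrCl limit or passes the transaminase limit is recorded as having had that event. A Group 2 candidate with the same event at enrolment is refused entry. A candidate who has already stopped BIC/F/TAF is not barred in so many words, but has no course of treatment left to follow.

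The plan keeps no list of all switchers, so these people leave no trace in the results. The week-48 proportion has no comparator and rests on about 20 subjects, so a reader could not tell sustained success from prior removal of failures. Correct timing of Group 2 visits would not help, because the question is who enters.

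**Working it through.** **Is there a figure to reproduce?** No. The target of 20 rests on feasibility, with no formula, power or margin. The one failure rate in the documents is the cited switch trial's 3/282 = 1.06%, which agrees with the stated 1%. It is virologic only and was not measured in transplant recipients.

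**Do the safeguards reach the missing people?**

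- Section 4.5: "Screen failures are defined as participants who consent to participate in the clinical trial but are not subsequently entered in the study". A switcher who failed and was never approached is not a screen failure.
- Section 11.2 records pre-enrolment adverse events, if related to the drug, only for those enrolled in Group 2.
- The laboratory and medication data around the switch (Section 3.1 and the footnote to the Section 6.1 schedule) are likewise collected from Group 2 subjects only.

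They show early events in people who entered, not people who were kept out.

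**Size of the shift.** Inputs:

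- q, the true failure rate by 48 weeks after the switch: 1.06% (cited trial) or 12% (assumption).
- w, the share of failures that occur before enrolment and keep the patient out: 50% or 75% (assumption).
- g, the Group 2 share of those enrolled: 4/20 = 0.20. The four comes from Section 2, where four of 37 patients were on TAF-containing regimens. The documents do not say these were BIC/F/TAF, or how many switched later.

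Failure rate seen in Group 2 = q(1 − w) / (1 − wq). Understatement of the pooled failure rate = g × (q − that rate).

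| q | w | Rate seen in Group 2 | Pooled understatement | Failures in 20 |
|---|---|---|---|---|
| 12% | 50% | 6/94 = 6.4% | 0.20 × 5.62 = 1.1 points | 0.22 |
| 12% | 75% | 3/91 = 3.3% | 0.20 × 8.70 = 1.7 points | 0.35 |
| 1.06% | 50% | 0.532/99.468 = 0.53% | 0.20 × 0.529 = 0.11 points | 0.02 |
| 1.06% | 75% | 0.266/99.202 = 0.27% | 0.20 × 0.796 = 0.16 points | 0.03 |

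The shift is proportional to g. Section 3.1 gives eighteen subjects instead of 20. With 4 of 18 (g = 0.222) the 12% rows become 0.222 × 5.62 = 1.2 and 0.222 × 8.70 = 1.9 points. If 10 of 20 were Group 2, they would be 0.5 × 5.62 = 2.8 and 0.5 × 8.70 = 4.4 points.

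**The case against.** The strongest reply is that the effect is narrow and probably small, in a descriptive pilot with no test or margin. Much of that stands, and it rules out several stronger readings that a reader might infer:

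- **Any fall in CrCl or rise in transaminases bars entry.** Only CrCl below 30 mL/min or ALT/AST above 5 × ULN does.
- **A patient who once failed can never enter.** Viral load looks back only 3 months, CrCl uses the latest creatinine, and Section 4.5 allows rescreening after a renal exclusion. Resolved events can enter, and the retrospective data would show some of them.
- **Every Group 2 subject adds bias.** No minimum time since the switch is set. For someone who switched days or weeks before enrolment, the 3-month window is mostly pre-switch.
- **The entry criteria are the same as the failure definitions.** The thresholds coincide, but virologic failure needs two values, and CrCl below 30 leads to a hold and evaluation, outside the five numbered events.
- **Placing Group 2 visits by stability is another entry bar.** Group 2 subjects are "inserted into the Schedule of Assessments at the discretion of the Principal Investigator based on stability" of viral load and tacrolimus levels. That text governs where an enrolled subject joins the schedule.
- **Half or more of the 20 will be Group 2.** No passage supports this. The only related figure is the four patients above.

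What the reply does not answer is that never-enrolled switchers are uncounted and that nothing separates the two groups in the reported proportion.

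**Conclusion.** The point holds in a limited form. For Group 2, enrolment-time eligibility selects on post-switch results, and the plan neither counts those it leaves out nor reports the group apart. The direction is known: it favours BIC/F/TAF on week-48 suppression, tolerability and renal safety.

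The size is not known, because the documents give neither the number in Group 2 nor a failure rate for this population. With four Group 2 subjects of 20, it is about 0.1–0.2 points at the cited 1% virologic rate and 1.1–1.7 points at an assumed 12%. It grows with the Group 2 share.

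These figures assume that every failure before enrolment keeps the patient out, so resolved events would make them smaller. They also count 48 weeks from the switch, which the protocol does not define for Group 2. The enrolment anchor for transaminases and the pooled reporting are my reading of text that is silent on both. The correction is worth making because it is cheap, not because a large bias has been shown.

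**What to change.** Add to Sections 3.1 and 10.1 wording such as: *The primary efficacy, tolerability and renal safety summaries include subjects who met the eligibility criteria before their first dose of BIC/F/TAF (Group 1). Group 2 is reported separately and descriptively, as results conditional on having remained on BIC/F/TAF and eligible at enrolment. Group 2 is retained for the pharmacokinetic analyses.* Entry and dispensing rules stay as they are.

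Optionally, and only if the ethics committee permits, report a chart count of all renal-transplant patients at the site who switched before identification. Give the number not enrolled and the reason: virologic failure by the two-value definition in Section 12, intolerance, renal, other, or declined. Place this beside the trial results, not in the trial denominator. Counting every non-enrolled switcher as a failure would misclassify single viral-load blips and non-clinical stops, and would put people who never consented into the primary proportion.

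The cost is a short text change and a smaller primary set. If four of 20 were Group 2 and all subjects were suppressed, the exact 95% lower limit would move from 0.025^(1/20) = 83.2% to 0.025^(1/16) = 79.4%. The chart count would add record review and an ethics submission.
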